## 10. Statistical Analysis

## 10A. Data Analysis

Primary analyses will be *intent-to-treat;* we will examine dose-response effects in secondary analyses. Primary tests will be 2-sided with  $\alpha$ =0.05. Site differences will be modeled with fixed effects. Descriptive statistics will include effect sizes and measures of clinical significance (i.e., area under the curve; number needed to treat) for all major comparisons. We will separate primary hypothesis (Aim 1) from remaining hypotheses (Aims 2-4). Standard post hoc procedures will be used to adjust for multiple comparisons when testing secondary hypotheses. There is no planned interim analysis. Analyses will adjust for baseline levels of dependent variables, gender, and yes/no history of suicide attempts. Consistent with CONSORT guidelines, we will pre-specify covariates and will not adjust for imbalance observed post hoc.

The original grant application stated that: "We will finalize and total data from each study phase that has been completed as they are completed (i.e., intake and 1-month follow-up will be complete by Month 32, 4-month follow-up will be complete by Month 35, 8-month follow-up will be complete by Month 39, and 12-month will be complete by Month 43). Given the timelines for data cleaning and recoding described above, intake and 1-month follow-up data will be available for analysis by Month 32, 4-month follow-up will be available for analysis by Month 35, 8-month follow-up data will be available for analysis by Month 39, and 12-month data will be available for analysis by the end of Month 43." Our timeline slid a little from this proposal due to recruiting another 3 months and waiting to see if anyone else would get out of jail. At this point, per the original analysis plan, we will close the assessment windows and begin data analysis for each wave as follows:

- Baseline: 4/12/19
- 4-week: 4/12/19 (all participants will be at least 4-weeks from their release date at this point)
- 16-week: 5/12/19 (all participants will be at least 16-weeks from their release date by this date)
- 34-week: 9/12/19 (all participants will be at least 34-weeks from their release date by this date)
- 52-week: 1/20/20 (all participants will be 52-weeks from their release date by this date)

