**Missing Data.** We will collect medical record and death record data on all participants. Self-reported count (e.g., suicide events) and historical (e.g., weekly LIFE ratings) data from missed assessments will be gathered at later follow-up assessments. We will use multiple imputation to deal with missing data. We will compare treatment conditions on rates of missingness and time to missingness and will test whether baseline characteristics are associated with missingness. Finally, we will perform a sensitivity analysis in which we impute extreme values for missing data to determine the sensitivity of analysis results to missing data.

**Outcomes.** Primary. We will test the hypothesis that, relative to SOC alone, SPI + SOC will result in fewer suicide events over the 52 week follow-up period, using ordinal logistic regression with lifetime suicide attempts events at baseline as a covariate. The analysis framework will be multivariate ordinal dependent variable regression. We begin with ordinal models because our simulations suggest the count outcome will not likely exceed 3. We will explore using different models such as zero-inflated Poisson or zero-inflated negative binomial with an offset defined by the length of follow-up and time in the community (as opposed to reincarcerated), and other reasonable approaches. Determination of the appropriate modeling will be determined using model selection (information) criteria and the determination will be made blind to the effect of the SIP intervention. Secondary. We will separately test the hypotheses that, relative to SOC alone, SPI + SOC will result in fewer suicide attempts, fewer weeks of active suicide ideation (per the LIFE calendar), lower severity of suicide ideation (C-

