Power. Our primary outcome (suicide events) is a composite of the number of suicide attempts (including suicide deaths), suicide behaviors (per the Columbia criteria), and suiciderelated hospitalizations. Previous trials of brief suicide risk reduction interventions in other at-risk populations have yielded relative risks of 1.6, 1.8, 57 1.8, 58 2.1, 59 and 2.6 60, 61 for suicide attempts  $(11.0 \text{ for suicide deaths}^{62})$ ,  $2.0^{60,61}$  and  $3.1^{209}$  for suicide behaviors, and  $1.8^{60,61}$  for hospitalization. This study is powered to detect an effect size at the lower end of the range of y/n effect sizes of successful similar studies, relative risk of 1.8 for any attempts, 2.0 for any behaviors, and 1.7 for any hospitalization (see below). In reality, our power will be better because we are measuring total number of each event, not just any event occurrence. Base rates. The literature provides information about base rates of suicide deaths among general populations of jail detainees, but not suicide events among jail detainees with suicide ideation. Therefore, we estimated control condition (base rate) event estimates among suicidal jail detainees conservatively as half the rates we observe in ED and inpatient studies. 57,60,61 This conservative estimate given our inclusion criteria of "yes" to C-SSRS item C4 or item C5 (some suicidal intent) or a suicide attempt in the month prior to enrollment is supported by rates of psychiatric observation (similar to inpatient hospitalization) for suicidality at jail entry (see D2.5). We express *clinical significance* using the area under the curve (AUC) statistic, following Kraemer. The AUC is flexible and has a direct and clinically relevant interpretation: the proportion of pairs, sampling one person exposed to the active treatment and another to the control, where the member of the pair exposed to SPI has a more favorable outcome profile. Our expected main effects translate into an AUC of 0.58, indicating that there is a 58% chance that a randomly selected participant from the SOC condition will have more suicide events than a randomly selected person from the SPI condition. This corresponds to a d=.28, meaning that our study is powered to detect small effects. This is the median effect size for suicide attempts reported in the literature, and we have super-adequate power to detect this effect (96.5%; see below). Estimation. We estimated power using Monte Carlo methods and 1001 replications per condition. Assuming: (1) the outcome is a total count of three outcomes [suicide attempts (including deaths), suicide behavior, and suicide related hospitalization] analyzed with ordinal logistic regression, (2) outcomes are correlated at 0.50 and have base rates of 10%, 18% and 12% in the control group and 5.5%, 9%, and 7% in the SPI group (where these percentages reflect cumulative annual incidence), and (3) a baseline sample of 800 released

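### Does the open-ended choice of primary model in Section 10A leave the primary test so undefined that the plan must change?

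*Combined protocol and SAP*

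**What the plan says.** Section 10A (Outcomes, Primary) states one hypothesis, that adding SPI to standard care lowers the number of suicide events over the follow-up year. It tests this "using ordinal logistic regression with lifetime suicide attempts events at baseline as a covariate". The ordinal model is a starting point: "We will explore using different models such as zero-inflated Poisson or zero-inflated negative binomial with an offset" for follow-up and community time, "and other reasonable approaches". The rule for choosing is "Determination of the appropriate modeling will be determined using model selection (information) criteria", with the safeguard that "the determination will be made blind to the effect of the SIP intervention" (SIP is evidently a slip for SPI).

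The general part of Section 10A adds "Primary tests will be 2-sided with" alpha 0.05, and "Analyses will adjust for baseline levels of dependent variables, gender, and yes/no history of suicide attempts". Section 10B calculates power for the ordinal model only. The outcome there is a sum of three components "analyzed with ordinal logistic regression, (2) outcomes are correlated at 0.50 and have base rates of 10%, 18% and 12% in the control group". For the SPI arm the assumed rates are 5.5%, 9% and 7%. The stated power is 96.5%.

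**The concern.** Three items are not written down: which information criterion is used, which models compete, and which treatment contrast carries the 0.05 test if a zero-inflated model wins. Such a model can hold two treatment coefficients. One concerns the odds of belonging to a group that never has events, the other the event rate among the rest. Blinded selection stops anyone picking a favourable model, but it does not say which of these coefficients decides the trial.

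This is the only confirmatory hypothesis, and the power figure belongs to one model. If the fallback were used and the wrong coefficient read, a trial planned at 96.5% power could have under 30%.

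**Working it through.** **Inputs.** Event rates, correlation, N = 800 and 78% evaluable are from Section 10B; 1:1 allocation is from Section 4A. Evaluable: 800 × 0.78 = 624, or 312 per arm.

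**1. The plan's own figure.** Simulate the 0-3 sum of three correlated yes/no outcomes and compare arms with the proportional-odds score test (tie-corrected Wilcoxon), two-sided 0.05, 100,000 replications.
- 0.50 as a latent correlation: 95.8% (plan: 96.5%).
- 0.50 as an observed (phi) correlation: 92.8%.

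**2. Which model is chosen** (latent, fits without treatment or covariates, 1,000 trials).
- AIC: ordinal 95%, ZIP 5%.
- BIC: ZIP 80%, ordinal 19%.
- The two criteria disagree in 76% of trials.
- Under phi, both keep ordinal in 99.8-100%.

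**3. Power if ZIP is always fitted** (latent, likelihood-ratio tests).

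| Treatment enters | Test | Power |
|---|---|---|
| both parts | count coefficient alone | 12.9% |
| both parts | zero coefficient alone | 25.8% |
| both parts | joint, 2 df | 91.4% |
| count part only | count coefficient | 94.0% |
| zero part only | zero coefficient | 94.9% |

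**4. Why the single coefficients fail.** The mean count is 0.10 + 0.18 + 0.12 = 0.40 in controls and 0.055 + 0.09 + 0.07 = 0.215 under SPI, a ratio of 0.54. The simulated share with any event is 0.2832 and 0.1643. The mean among those with an event is therefore 0.40/0.2832 = 1.41 and 0.215/0.1643 = 1.31. A ZIP fitted by arm solves λ/(1 − e^(−λ)) = that mean, which gives λ ≈ 0.735 and 0.564. The share outside the zero class is 0.40/0.735 = 0.54 and 0.215/0.564 = 0.38. The overall ratio thus splits into 0.38/0.54 ≈ 0.70 and 0.564/0.735 ≈ 0.77, and 0.70 × 0.77 ≈ 0.54. Each part carries only some of the effect, and both are estimated from the same zeros.

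**5. Whole procedure** (blind selection, then test; 10,000 trials per cell; ordinal alone 95.6%).
- BIC, latent: overall mean ratio 95.4%; joint test 93.0%; zero part 39.7%; count part 28.5%; either coefficient 48.8%.
- AIC, latent: 92.1-95.5% under every reading.
- Phi: 92.5-92.7%.
- Type I error: 3.2-5.1% under every reading.

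Hand check of the two lowest cells, using this run's always-ZIP powers of 26.3% (zero part) and 12.2% (count part):
- Zero part: 0.80 × 26.3% + 0.20 × 95.6% = 40.2% (simulated 39.7%).
- Count part: 0.80 × 12.2% + 0.20 × 95.6% = 28.9% (simulated 28.5%).

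**6. Covariates.** The plan requires them, so the intercept-only selection in steps 2 and 5 is a simplification. With four null binary covariates (latent, BIC, 220 trials), ZIP is chosen in 75% if they enter the count part only and in 0% if they enter both parts. If two of the four are prognostic (assumed 0.3 SD on the latent scale, count part only, 150 trials), ZIP is chosen in 42%.

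**The case for a change.** The case for a change is that blinding governs which model is picked, not which contrast is read, and the two-part output appears only once treatment is added. If all five contrasts in step 3 were searched after unblinding, at least one would be significant under the null in 12.1% of trials, although each alone rejects in 4.4-5.0%. The plan settles neither AIC against BIC nor latent against observed correlation, so the benign case is not guaranteed. Writing the rule down costs only wording.

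Some of this stands. The three items are indeed missing, and the effect measure would differ by model: an odds ratio without an offset, or a rate ratio per unit of community time. But nothing in the plan licenses a search over contrasts. The hypothesis is stated once, as fewer events in total, and a coefficient adjusted for the other half of the model does not test that. The low-power cells also rest on counts capped at 3, whereas Section 9 counts every occurrence.

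Nor is there a clearly better rule to insert.
- **Blinded selection plus an overall mean ratio.** With assumed repeat events, power is 80-93%, against 92-95% for the ordinal test alone.
- **Ordinal model as the only confirmatory test.** This drops the community-time offset. With 30% re-arrest in both arms (Section 13A; 20-90% of the year left in the community is assumed), power is 93.4%, against 93.0% for the offset rate ratio. If SPI cut re-arrest to an assumed 20%, it is 88.3% against 93.1%.

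Each option gives something up, and the plan's blinded, data-led choice is a fair way to weigh them.

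**Conclusion.** The gap is real but is one that analysts fill sensibly, and no change is required. Type I error is not at risk under any single reading fixed in advance. On the plan's rates, the readings that test whether SPI reduces events keep the procedure at about 92-96% power, close to the stated 96.5%. The fall to about 28-49% needs all of these together: a latent 0.50 correlation, BIC, covariates absent or in the count part only, treatment in both parts of the model, and one partial coefficient (or either one) taken as the primary result.

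These figures assume 312 per arm, a 0-3 count and no offset; the power figures also assume no covariates. The selection percentages are therefore illustrative. The authors could state the criterion and contrast when they finalise the analysis, but the trial's conclusion does not depend on it.

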## 3. Subjects

## 3A. Description of Study Population

Our target population is suicidal pretrial jail detainees who are returning to the community. We will exclude individuals who expect to be sentenced to prison. However, we expect 6-8% of the pretrial jail detainee participants we consent who do not expect to be sentenced to prison will be sentenced anyway. Although some of these individuals will not leave jail for the community (i.e., will go directly to prison, not home), we found that some individuals receive very short sentences within jail (≤30 days) prior to release. This timeframe for release is similar to that for those who are not sentenced following their court dates because there is some variability in time spent in jail awaiting trial. Therefore, individuals who are sentenced for ≤30 days will remain eligible for the study as they can participate in post-release study activities within a similar timeframe as those who do not get sentenced. This is a standard approach taken in other re-entry studies (e.g., R01 AA021732; U01DA01619113) that must consent participants when their sentencing or release status is still unknown. Sentencing will occur independent of study condition, so their exclusion from analysis (no "at-risk" community months) will be unlikely to influence internal validity. We will follow all remaining participants who are released from jail to the community after the index incarceration through the 52-week post-release period regardless of reincarceration, continued participation in SPI or SOC, or subsequent suicide attempts or hospitalizations. Of the 92-94% of participants who are released from jail to the community after the index incarceration, we conservatively estimate that postrelease follow-up rates will be 82% at 4 weeks, 80% at 16 weeks, 75% at 34 weeks, and 70% at 52 weeks, with 85% of participants providing data for at least one post-release follow-up interview. Post-release follow-up rates in previous and ongoing studies have been higher than this. Therefore, we expect that 78% (85% of the 92% who are released from jail) of the 800 enrolled participants will provide evaluable follow-up data. Count (e.g., suicide events) data from missed follow-ups will be gathered at later follow-ups when they occur, and we will collect medical record and death record data on all eligible (i.e., released) participants. Study dropouts will not be replaced; attrition has been accounted for in power and sample size estimates.

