#### 9. Outcome Measures

Assessments will take place at baseline, and at 4, 16, 34, and 52 weeks post-release. Baseline assessments (including informed consent, locator, and release of information paperwork) will take place in person at the jail; RAs will offer to read each study assessment aloud. Follow-up assessments will take place by telephone (the most feasible way to do follow-ups with this population), unless a participant is reincarcerated, in which case the follow-up assessment will take place in person at the jail/prison. If a participant is in a residential treatment facility, the follow-up assessment may take place by phone or in person at the residential treatment facility.

Table C1: Assessments	Туре	Time (min)	Baseline	4, 16, 34, and 52 week Follow-up
Suicidal Ideation and Behavior				
Columbia Suicide Severity Rating Scale (C-SSRS) 181	Interview	20	X	X
L.I.F.E. 182 – suicidal ideation and behavior	Interview	10		X
Suicide deaths: record review (state/national death registry)	Objective	0		X
Hospitalizations: Tx History Interview, record review (local hospitals)	Objective	0	X	X
Psychiatric Symptoms:				
DSM-5 Cross-Cutting Measure	Self-Report	7	X	X
K6	Self-Report	1	X	X
LEC/PCL	Self-Report	7	X	X
AUDIT and DUDIT	Self-report	7	X	X
Overdose	Self-report	10	X	X
Functioning: VR-12  from RAND Medical Outcomes Study	Self-Report	3	X	X
Hypothesized Mechanisms				
Treatment utilization: Treatment History Interview 	Interview	8	X	X
Belongingness: Interpersonal Needs Questionnaire-12 	Self-Report	5	X	16 ,34, 52 only
Suicide-related problem-solving: Suicide Related Coping Measure	Self-Report	5	X	16, 34, 52 only
Diagnosis: Mini International Neuropsychiatric Interview (MINI)  : lifetime psychosis, mania/hypomania, major depressive episode	Interview	10		4 week only
Safety Plan use in the context of Substance Abuse	Interview	10		52 only
Total patient time for interview (min)			Consent[contact]

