Primary outcome. Suicide Events is a composite score consisting of the total number of occurrences of any of the following in the year after jail release: (a) attempted suicide (includes suicide deaths), (b) suicide behaviors (preparatory acts, aborted or interrupted suicide attempts), as defined using the Columbia criteria, 181,188 and (c) suicide-related hospitalizations. We will use the Treatment History Interview (THI189) as well as hospital records to track the number of subsequent hospitalizations and reasons for these admissions. Suicide event data will be assessed using data collected from all possible sources, including follow-up assessments (C-SSRS, THI), (b) hospital chart reviews, and (c) state/national registries. Data from all sources will be reviewed by 2 research team members for congruence. Disagreements will be reviewed and adjudicated by ... All reports will be classified using C-SSRS criteria. The C-SSRS is the recommended measure of suicidal ideation and behaviors in the NIH PhenX Toolkit as a core data element in all clinical trials for suicide prevention. Although it will not be included in our suicide event composite, we will also track implementation of rescue procedures (e.g. calling Emergency Services/police, breaking confidentiality to inform clinician of high suicide risk) during SPI phone calls or study assessments and compare conditions on this variable.

**Secondary outcomes.** Suicide Attempts. We will separately assess and evaluate total number of subsequent attempts using the procedures described above. Weeks of active suicidal ideation during the follow-up period will be operationalized using the Longitudinal Interval Follow-

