Up Evaluation (LIFE;190). At each assessment point, we will ask participants to rate their level of suicidal ideation in the weeks since the last assessment on a 6-point psychiatric status rating scale. This LIFE method yields weekly scores and allows us to examine both the occurrence and chronicity of suicidal ideation over the follow-up period. The LIFE calendar will also be used to assess time to first suicide event. As in this study, the LIFE is often administered by phone (i.e. 191, 192). Severity of suicide ideation. We will also assess severity of suicidal ideation using the Suicidal Intensity subscale from the C-SSRS. Psychiatric symptoms will be assessed using the DSM-5 Level 1 Cross-Cutting Symptom Measure. This measure was chosen because it is the recommended measure of broad psychopathology in the Tier 1 Core for Mental Health research in the NIH PhenX Toolkit, performed well psychometrically in the DSM-5 Field Trials, and is comprehensive yet brief. Substance use will be measured using the Alcohol Use Disorders Identification Test (AUDIT) and the Drug Use Disorders Identification Test (DUDIT). These measures were chosen as they are well validated, brief measures that have been used in several countries and clinical settings, and are cross-referenced as relevant common data elements in the Suicide Specialty Collection of the NIH PhenX Toolkit. As part of the supplement, we also will assess Overdose through a series of questions asked during baseline and follow-up assessments. Overall functioning will be measured using the VR-12, 183 a brief, widely used measure of physical and mental health functioning that also provides our secondary costeffectiveness measure (see below).

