Hypothesized mechanisms of SPI effects. We define treatment utilization (primary) as the number of outpatient mental health and substance use visits attended in the community in the 3 months prior to baseline or since the last assessment, as indexed by the THI. Belongingness (exploratory) will be assessed using the Interpersonal Needs Questionnaire (INQ-12). 185,193 Suicide-related problem-solving (exploratory) will be assessed using a standard checklist of suicide safety behaviors and asking whether each was utilized during the most suicidal period since the last interview (identified on the C-SSRS). The checklist includes two subscales to minimize assessment reactivity: the sum of the number of recommended (e.g., call a friend) and the sum of the number of not recommended (e.g., use drugs) responses to suicidal thoughts or urges. These are the most direct, objective measures possible given the time-pressed, chaotic jail setting for baseline assessments and telephone follow-up.

Additional outcomes. Suicide deaths. Given the low incidence of suicide deaths, even in this high risk sample, we do not expect to have sufficient numbers of suicide deaths (separate from the suicide event composite) for meaningful analyses. However, we will track number of suicide deaths using all possible data sources, including hospital records and reviews of state and national death registries. Although our intervention does not target re-arrest directly, it is possible that by increasing service linkage, SPI could reduce re-arrest; therefore, we will assess number of re-arrests and compare conditions on this variable. We will also track days incarcerated in the year after the index release to weight participants by time in the community for other analyses. In addition, a brief questionnaire was added to the end of the study to collect open-ended participant feedback about his/her experience in the study.

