SSRS scores), longer time to first suicide event, fewer psychiatric symptoms (DSM-5 Cross Cutting Measure scores), and better psychosocial functioning (SF-12 scores). For normally distributed variables (i.e., C-SSRS, DSM-5 Cross Cutting, SF-12, AUDIT, DAST-10), analyses will use a generalized linear mixed model framework for multilevel data (e.g., SAS/proc mixed, HLM) with baseline scores as covariates. For count data (i.e., number of suicide attempts, weeks of active suicide ideation), analyses will use Poisson-class regression methods 204,205 (e.g., negative binomial regression) and will include appropriate tests for zero-inflation and overdispersion and offset defined by length of time of follow-up and time in the community. Time to suicide event will be analyzed using time-to-event models, beginning with semi-parametric Cox regression models assuming proportionality assumptions are met, otherwise discrete time or parametric continuous time survival models will be used. Model choice will be informed by information criteria and decisions made blind to intervention assignment. Exploratory, Although not part of formal hypotheses, we will also compare conditions on (1) rates of death by suicide, (2) number of re-arrests, and (3) number of emergency referrals generated as part of study assessment safety procedures. Supplement. We will examine whether SPI+SOC has a differential effect on overdose rates and on overdose versus non-overdose suicide attempts. Qualitative data also will be collected at the end of the 12-month follow-up interview to better understand how individuals used or did not use their Safety Plan in the context of substance abuse.

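### Does the undefined offset for suicide attempts and ideation weeks distort the treatment rate ratio?

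*Combined protocol and SAP*

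**What the plan says.** Section 10A assigns the secondary counts (suicide attempts, weeks of active ideation) to Poisson-class regression with an "offset defined by length of time of follow-up and time in the community". For the primary outcome, the first-line model is ordinal logistic regression with no stated offset. The alternative zero-inflated count models come "with an offset defined by the length of follow-up and time in the community (as opposed to reincarcerated"). Section 9 adds that the study will "track days incarcerated in the year after the index release to weight participants by time in the community for other analyses".

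The outcome definitions in section 9 carry no matching restriction. Attempts are the "total number of subsequent attempts using the procedures described above". The ideation outcome is "Weeks of active suicidal ideation during the follow-up period", built from LIFE interviews in which "we will ask participants to rate their level of suicidal ideation in the weeks since the last assessment". Follow-up runs "through the 52-week post-release period regardless of reincarceration" (section 3A). Interviews are by telephone "unless a participant is reincarcerated, in which case the follow-up assessment will take place in person at the jail/prison" (section 9).

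**The concern.** An offset is one exposure time per person. Here two times are named, so two analysts could both follow the plan and fit different models. The contrast with reincarceration, and the tracking of custody days, suggest that exposure is follow-up minus custody. The counts, as described, seem to include what happens in custody. On that reading a re-jailed participant's events are divided by too little time. For ideation the rate can become impossible: 20 ideation weeks over 4 community weeks is 5 weeks per week.

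Custody time also arises after randomisation, and section 9 allows that SPI could lower re-arrest. If it did, SOC participants would have the more inflated rates and the ratio would fall below 1, in favour of SPI. The two secondary counts would be affected, and so would the primary outcome if an alternative count model replaced the ordinal one.

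**Working it through.** The plan gives no figure for the offset or for the secondary counts. Its only related figure, 96.5% power (section 10B), concerns the ordinal model. It is approximately reproduced (95.6% by simulation, 312 per arm, 0.50 taken as a latent correlation) and does not depend on the offset.

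**Inputs**
- Share re-jailed: SOC p0 = 0.30, borrowed from the 12-month re-arrest figure in section 13A, which is re-arrest in general jail populations and not custody. SPI p1 = 0.20 or 0.30 (assumed).
- Mean custody m among those re-jailed: 1, 3, 4.3 (30 days), 8, 19 and 27 weeks (assumed). Sections 1A and 1C give a few days, median 4, but for the index stay.
- r = risk in custody divided by risk in the community: 1 and 0.5 (assumed), and 35/128 = 0.27 from the suicide death rates in section 1B. Over that section's range, r runs from 35/204 = 0.17 to 35/41 = 0.85. Death rates are a rough proxy for attempts and a weaker one for ideation.

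**Formulas**, with no SPI effect in either setting and c = p × m (c1 for SPI, c0 for SOC)
- Mismatched (all events over community time): RR = [(52 − c1 + r·c1)/(52 − c1)] / [(52 − c0 + r·c0)/(52 − c0)].
- Total time (all events over 52 weeks): RR = (52 − c1 + r·c1)/(52 − c0 + r·c0).
- Matched community (community events over community time): RR = 1 for every r and m.

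**Example**, m = 19 and r = 0.27: c1 = 0.20 × 19 = 3.8 and c0 = 0.30 × 19 = 5.7. Mismatched: (49.24/48.2)/(47.86/46.3) = 0.988. Total time: 49.24/47.86 = 1.029.

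**Results**, 30% against 20% re-jailed, true ratio 1

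| Mean custody (weeks) | Mismatched, r = 1 | Mismatched, r = 0.5 | Mismatched, r = 0.27 | Total time, r = 0.5 | Total time, r = 0.27 |
|---|---|---|---|---|---|
| 1 | 0.998 | 0.999 | 0.999 | 1.001 | 1.001 |
| 3 | 0.994 | 0.997 | 0.998 | 1.003 | 1.004 |
| 4.3 | 0.992 | 0.996 | 0.998 | 1.004 | 1.006 |
| 8 | 0.984 | 0.992 | 0.996 | 1.008 | 1.012 |
| 19 | 0.961 | 0.979 | 0.988 | 1.019 | 1.029 |
| 27 | 0.942 | 0.969 | 0.982 | 1.028 | 1.043 |

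At r = 1 the total-time ratio is 1.000 throughout. With 30% re-jailed in both arms, every entry is 1.000. The two approaches lie about equally far from 1 at r = 0.5. Below that the mismatched ratio is nearer 1, above it the total-time ratio is.

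**Individual inflation**, (52 − k + r·k)/(52 − k) for k custody weeks: at r = 1 it is 1.02, 1.06, 1.09 and 1.18 for k = 1, 3, 4.3 and 8.

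**Negative binomial models.** These weight people differently from the pooled formula.
- Identical stays of 8, 19 and 27 weeks, r = 1: attempts (assumed mean 0.15, dispersion 3) give 0.984, 0.957, 0.934. Ideation weeks (assumed mean 10, dispersion 2) give 0.983, 0.951, 0.919.
- Simulated variable stays, r = 1, 30% against 20%, 312 per arm: for attempts (assumed mean 0.13, dispersion 2), 0.96 at a mean of 90 days and 0.95 at 180 days, with rejection of 4.8% and 5.8%. For ideation weeks (assumed mean 8, dispersion 1.5), 0.95 and 0.79, with rejection of 5.5% and 13.3%.
- In the same simulations, the total-time and matched community analyses both gave 0.99 to 1.01.

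**The case for a change.** The strongest case for acting is that the rate is undefined as written and, on the natural reading, incoherent whatever the balance between arms. Stating one formula would take a sentence or two and no new data. The ideation simulation shows that the error need not be trivial: with a mean of 180 days in custody among those re-jailed, 30% against 20%, the false-positive rate was 13.3%.

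The missing formula stands as a fact. The rest is weaker. The passages on counting describe data collection and follow-up; none says that custody events enter a model of community rates. Sections 3A and 10B describe time at risk as months in the community, although about people never released, and sections 9 and 10A point the same way. An analyst who takes community time as exposure would naturally restrict the count to it, and that removes the mismatch. Doing so needs dated events and custody spells, and section 9 plans only custody days.

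The large ideation figures need an arm difference and stays of about half a year, neither of which the documents support; they give no custody length after re-arrest at all.

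Nor is total follow-up clearly better. It drops the community time that the plan names and carries any SPI effect on custody into the ratio. One may call that a real difference in yearly outcomes, but that is a choice of estimand. Detection also differs: record review covers local hospitals and emergency rooms, while jail medical records are planned only for comparing screening results (sections 4D and 9). Non-fatal events in custody would therefore rest mainly on self-report, which is a fair reason to prefer community exposure.

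**Conclusion.** No change to the plan follows. What is established is an unstated formula in two secondary count models and in the alternative count models for the primary outcome. The numerator–denominator error is only one reading of it. Analysts can settle the exposure, and match the count to it, when they build the models; section 10A already has model choice made blind to intervention assignment. Community events over community time, and all events over observed follow-up, are both coherent. The documents do not settle which should lead, and statisticians would differ.

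Even on the mismatched reading, the pooled ratio shifts by less than 1% for mean stays up to 30 days and by at most about 6% at 27 weeks, given 30% against 20% re-jailed and equal risk in custody. It does not shift at all when custody time is equal by arm. Ideation weeks could shift more under long, variable stays. The arm difference, the custody lengths and the risk ratio are assumptions, so these sizes are illustrative. The ordinal primary analysis and its 96.5% power figure do not depend on the offset.
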